8.1.2 Nivolumab and Ipilimumab Dose Discontinuation

For participants who receive nivolumab in combination with ipilimumab and trametinib, study treatment should be permanently discontinued for the following:

- Any Grade 2 drug-related uveitis, eye pain or blurred vision that does not respond to topical therapy and does not improve to Grade 1 severity within the re-treatment period OR requires systemic treatment
- Any Grade 3 non-skin, drug-related adverse event lasting > 7 days, or recurs, with the following exceptions for laboratory abnormalities, diarrhea, colitis, neurologic toxicity, drug-related uveitis, pneumonitis, bronchospasm, hypersensitivity reactions, infusion reactions, and endocrinopathies:
 - Grade 3 drug-related diarrhea, colitis, neurologic toxicity, uveitis, pneumonitis, bronchospasm, myocarditis, hypersensitivity reaction, or infusion reaction of any duration requires discontinuation
 - Grade 3 drug-related endocrinopathies, adequately controlled with only physiologic hormone replacement do not require discontinuation. Adrenal insufficiency requires discontinuation regardless of control with hormone replacement.
 - Grade 3 drug-related laboratory abnormalities do not require treatment discontinuation except:
 - ◆ Grade 3 drug-related thrombocytopenia > 7 days or associated with bleeding requires discontinuation
 - ◆ Any drug-related liver function test (LFT) abnormality that meets the following criteria require discontinuation:
 - Grade \geq 3 drug-related AST, ALT or Total Bilirubin requires discontinuation*

- Concurrent AST or ALT $> 3 \times$ ULN and total bilirubin $> 2 \times$ ULN

* In most cases of Grade 3 AST or ALT elevation, study treatment(s) will be permanently discontinued. If the investigator determines a possible favorable benefit/risk ratio that warrants continuation of study treatment(s), a discussion between the investigator and the BMS Medical Monitor/designee must occur.

- Any Grade 4 drug-related adverse event or laboratory abnormality (including but not limited to creatinine, AST, ALT, or Total Bilirubin), except for the following events which do not require discontinuation:
 - Grade 4 neutropenia ≤ 7 days
 - Grade 4 lymphopenia or leukopenia or asymptomatic amylase or lipase
 - Isolated Grade 4 electrolyte imbalances/abnormalities that are not associated with clinical sequelae and are corrected with supplementation/appropriate management within 72 hours of their onset
 - Grade 4 drug-related endocrinopathy adverse events, such as, hyper- or hypothyroidism, or glucose intolerance, which resolve or are adequately controlled with physiologic hormone replacement (corticosteroids, thyroid hormones) or glucose-controlling agents, respectively, may not require discontinuation after discussion with and approval from the BMS Medical Monitor/designee.
- Any event that leads to delay in dosing lasting > 10 weeks from the previous dose requires discontinuation, with the following exceptions:
 - Dosing delays to allow for prolonged steroid tapers to manage drug-related adverse events are allowed.
 - Dosing delays lasting > 10 weeks from the previous dose that occur for non-drug-related reasons may be allowed if approved by the BMS Medical Monitor/designee. Prior to re-initiating treatment in a participant with a dosing delay lasting > 10 weeks, the BMS Medical Monitor/or designee must be consulted. Tumor assessments should continue as per protocol even if dosing is delayed. Periodic study visits to assess safety and laboratory studies should also continue every 4 weeks or more frequently if clinically indicated during such dosing delays.
- Any adverse event, laboratory abnormality, or intercurrent illness which, in the judgment of the Investigator, presents a substantial clinical risk to the participant with continued nivolumab + ipilimumab dosing.

Any criteria leading to the discontinuation of nivolumab, ipilimumab, or trametinib as part of the triplet investigative regimen in Parts 1B and 2 will require discontinuation of the entire regimen.

8.1.3 Trametinib Dose Discontinuation

A maximum of 2 trametinib dose level reductions are allowed for Part 1 and Part 1A. Only 1 dose level reduction is permitted for Parts 1B and 2. If a third dose level reduction is required for Part 1 or 1A, or dose reduction below 1.0 mg per day is required, study treatment should be permanently discontinued. In addition, discontinue trametinib permanently for the following:

- Any event that leads to delay in dosing for > 10 weeks from the previous dose requires discontinuation with the following exception:
 - Dosing delays > 10 weeks that occur for non-drug-related reasons may be allowed if approved by the BMS Medical Monitor. Prior to re-initiating treatment in a subject with a dosing delay lasting > 10 weeks, the BMS Medical Monitor must be consulted. Tumor assessments should continue as per protocol even if dosing is delayed.
- Any AE, laboratory abnormality, or intercurrent illness which, in the judgment of the investigator, presents a substantial clinical risk to the subject with continued treatment

Any criteria leading to the discontinuation of nivolumab, ipilimumab, or trametinib as part of the triplet investigative regimen in Parts 1B and 2 will require discontinuation of the entire regimen.

Refer to [Appendix 6](#) for additional dose discontinuation criteria.

8.1.4 Regorafenib Dose Discontinuation

Discontinue regorafenib permanently for any of the following (local product label and institutional guidelines should be followed if they are more conservative):

- Failure to tolerate 80 mg dose
- Any occurrence of AST or ALT > 20× ULN
- Any occurrence of AST or ALT > 3× ULN with concurrent bilirubin > 2× ULN, except in participants with Gilbert's syndrome
- Re-occurrence of AST or ALT > 5× ULN despite dose reduction to 120 mg
- Gastrointestinal perforation or fistula
- Severe or life-threatening hemorrhage
- Reversible posterior leukoencephalopathy syndrome
- Wound dehiscence
- For any Grade 4 adverse reaction; only resume if the potential benefit outweighs the risks
- Any event that leads to delay in dosing for > 10 weeks from the previous dose requires discontinuation with the following exception:
 - Dosing delays > 10 weeks that occur for non-drug-related reasons may be allowed if approved by the BMS Medical Monitor. Prior to re-initiating treatment in a subject with a dosing delay lasting > 10 weeks, the BMS Medical Monitor must be consulted. Tumor assessments should continue as per protocol even if dosing is delayed.
- Any AE, laboratory abnormality, or intercurrent illness which, in the judgment of the investigator, presents a substantial clinical risk to the subject with continued treatment

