7.1.4.2 Cohort 5 Regorafenib

In Cohort 5, participants will receive regorafenib at the approved dose per local product label until progression, unacceptable toxicity, withdrawal of consent, whichever occurs first. Participants should begin study treatment within 3 calendar days of treatment randomization.

Table 7.1.4.2-1: Recommended Dose of Regorafenib in Part 2 (Cohort 5)

Study Treatment	Every Cycle till the End of Treatment (28 day/4 week per cycle)
Regorafenib 160 mg ^a	Orally, once daily for the first 21 days of each 28-day cycle

^a The recommended dose of regorafenib is 160 mg. Refer to local product label and institution guidelines.

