7.4.6 Dose Modification for Regorafenib

If dose modifications are required, reduce the dose in 40 mg (1 tablet) increments; the lowest recommended daily dose of regorafenib is 80 mg daily. The following dose modification is provided as a recommendation. Local product labels and/or institutional guidelines should be followed if they are more conservative than the recommendations below.

Interrupt regorafenib for the following:

- Grade 2 hand-foot skin reaction (HFSR) [palmar-plantar erythrodysesthesia (PPES)] that is recurrent or does not improve within 7 days despite dose reduction; interrupt therapy for a minimum of 7 days for Grade 3 HFSR (refer to [Table 7.4.6-2](#) for additional requirements)
- Symptomatic Grade 2 hypertension
- Any Grade 3 or 4 adverse reaction
- Worsening infection of any grade
- Reduce the dose of regorafenib to 120 mg:
 - For the first occurrence of Grade 2 HFSR of any duration (refer to [Table 7.4.6-2](#) for additional requirements)
 - After recovery of any Grade 3 or 4 adverse reactions except infection

- For Grade 3 AST/ALT elevation, only resume if the potential benefit outweighs the risk of hepatotoxicity (refer to Table 7.4.6-1 for additional requirements)

Reduce the dose of regorafenib to 80 mg:

- For re-occurrence of Grade 2 HFSR at the 120 mg dose (refer to [Table 7.4.6-2](#) for additional requirements). After recovery of any Grade 3 or 4 adverse reaction at the 120 mg dose (except hepatotoxicity or infection)

Table 7.4.6-1: Recommended Measures and Dose Modifications in Case of Drug-related Liver Function Test Abnormalities

Observed Elevations of ALT and/or AST	Occurrence	Recommended Measures and Dose Modification
≤ 5 times ULN (maximum Grade 2)	Any occurrence	Continue regorafenib treatment. Monitor liver function weekly until transaminases return to < 3 times ULN (Grade 1) or baseline.
> 5 times ULN ≤ 20 times ULN (Grade 3)	1st occurrence	Interrupt regorafenib treatment. Monitor transaminases weekly until they return to < 3 times ULN or baseline. Restart: If the potential benefit outweighs the risk of hepatotoxicity, re-start regorafenib treatment, reduce dose by 40 mg (1 tablet), and monitor liver function weekly for at least 4 weeks.
	Re-occurrence	Discontinue treatment with regorafenib permanently.
> 20 times ULN (Grade 4)	Any occurrence	Discontinue treatment with regorafenib permanently.

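### Section 7.4.6's regorafenib reduction to 120 mg, as worded, takes in Grade 4 AST/ALT elevation at 160 mg, for which Table 7.4.6-1 and Section 8.1.4 require a permanent stop; for other Grade 4 reactions the two sections set different defaults

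*Combined protocol and SAP*

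**What the plan says.** Cohort 5 starts at the dose in Table 7.1.4.2-1: "The recommended dose of regorafenib is 160 mg. Refer to local product label and institution guidelines".

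Section 7.4.6 opens by calling its scheme a recommendation that gives way to a more conservative local label or institutional guideline. Under "Interrupt regorafenib for the following" it lists any Grade 3 or 4 adverse reaction. It then gives two reduction steps:

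- **To 120 mg:** "After recovery of any Grade 3 or 4 adverse reactions except infection". A separate item here attaches a benefit-risk condition, and a pointer to Table 7.4.6-1, to Grade 3 AST/ALT elevation only.
- **To 80 mg:** "After recovery of any Grade 3 or 4 adverse reaction at the 120 mg dose (except hepatotoxicity or infection" (the bracket closes there).

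Table 7.4.6-1, in the same section, has a row for AST/ALT above 20 times ULN, labelled Grade 4, at any occurrence. Its action is "Discontinue treatment with regorafenib permanently".

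Section 8.1.4 is headed "Discontinue regorafenib permanently for any of the following", again subject to more conservative local guidance. The list includes "Any occurrence of AST or ALT > 20× ULN", with no route back to treatment. A separate item reads "For any Grade 4 adverse reaction; only resume if the potential benefit outweighs the risks".

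Two other passages bear on precedence. Section 8.1 says participants must stop investigational product when criteria in Sections 8.1.1 to 8.1.4 are met, and Table 7-1 classes regorafenib as investigational product. Section 7.4 sends an investigator managing a regorafenib reaction to the local label, institutional guidelines and Section 7.4.6. It does not mention Section 8.1.4.

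**The concern.** Two instructions for one event in a dose-modification scheme are a participant-safety matter, because they concern whether someone is re-exposed after a Grade 4 reaction. The liver case is the sharper one: a general item in Section 7.4.6 provides for dosing after recovery, while a specific row of that section's own table and a specific item in Section 8.1.4 do not.

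The data are also touched. Section 10.3.2 lists adverse events leading to discontinuation as a safety endpoint. If two sites handle the same reaction under different passages, one records a discontinuation and the other an interruption with dose reduction. Section 9 allows no waivers, so a site that follows one passage could be recorded as deviating from the other.

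**Working it through.** The plan gives no figure to reproduce. The check sets the passages side by side for each Grade 4 situation.

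| Situation | Section 7.4.6 lists | Table 7.4.6-1 | Section 8.1.4 |
|---|---|---|---|
| AST/ALT above 20 times ULN, on 160 mg | Interrupt; 120 mg after recovery (only infection exempt) | Permanent stop | Permanent stop; the liver item has no resume clause |
| AST/ALT above 20 times ULN, on 120 mg | Interrupt; excluded from the 80 mg item | Permanent stop | Permanent stop |
| Other Grade 4, not infection, on 160 mg | Interrupt; 120 mg after recovery, no benefit-risk condition | Not covered | Permanent-stop list; resume only on a benefit-risk judgement |
| Other Grade 4, neither liver nor infection, on 120 mg | Interrupt; 80 mg after recovery, no benefit-risk condition | Not covered | As the row above |
| Grade 4 infection | Interrupt; exempt from both reduction items | Not covered | Falls under the general Grade 4 item |
| Cannot tolerate 80 mg | No lower recommended dose | Not covered | Permanent stop |

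**Liver, 160 mg (row 1).** The 120 mg item covers Grades 3 and 4 and exempts infection alone, so this event is inside it. The table and Section 8.1.4 agree with each other and disagree with that item. Row 2 shows the same event one step down, where the exemption is present and no conflict arises. The mismatch within Section 7.4.6 is therefore confined to the step from 160 mg to 120 mg. The pointer to the table does not help, because it is attached to Grade 3 only.

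**Other Grade 4 (rows 3 and 4).** Both sections contemplate further dosing. In Section 8.1.4 stopping is the default, and resumption is an exception that needs a judgement. In Section 7.4.6 interruption is the default, a lower dose follows recovery, and no judgement is stated. The Section 8.1.4 item also sits awkwardly in its own list, since it offers a way back under a heading that says the stop is permanent. On its words this general item takes in Grade 4 AST/ALT as well, although the specific liver item carries no such clause.

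**Scale.** Section 5.1.3 plans about 40 participants on regorafenib. One participant classified differently moves a Cohort 5 rate by 1/40 = 2.5 percentage points. The documents give no Grade 4 rate for regorafenib, so no count can be derived.

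**Timing.** Section 6 closes enrollment on 30-Nov-2022, and Amendment 04 is dated 03-May-2023, about 5 months later. Table 3.2.2-1 gives median PFS of 1.9 months on regorafenib, and Section 7.1.4.2 treats until progression at most. Assuming exponential progression, the share still progression-free after 5 months is 2^(-5/1.9) = 2^(-2.63) = 0.16. Even if all 40 had started on the last enrollment day, that is 0.16 × 40, or about 6 participants. Earlier starters lower it.

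**The case against.** The strongest reply is that the sections can be read in sequence: Section 7.4.6 says hold, Section 8.1.4 sets the condition for resuming, and Section 7.4.6 supplies the dose if dosing resumes. A reduction after recovery names a dose step; it does not order a restart. For Grade 4 reactions other than liver toxicity this reading is available, and it reduces that part to a difference of default and condition. It fails for Grade 4 AST/ALT at 160 mg, because the table and the liver item in Section 8.1.4 leave nothing to resume.

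The second reply is hierarchy. Section 8.1 is mandatory and Section 7.4.6 is a recommendation; for the liver, two specific thresholds stand against one general item lacking an exemption. A careful reader would probably let Section 8.1.4 and the table prevail. That is a strong indication, but no sentence states it. The clauses about more conservative guidance rank local labels and institutional guidelines against the protocol, not one protocol section against another. The rule in Section 7.4 to follow the most conservative guideline concerns the nivolumab and trametinib combinations. Section 7.4's regorafenib signpost leads only to the recommendation.

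Third, local variation is part of the Cohort 5 design, the primary endpoint is ORR, and adverse events leading to discontinuation are summarised descriptively. This stands: no effect on an efficacy conclusion has been shown, and not all site-to-site variation would come from this wording. The timing calculation also stands as a limit on how many participants a change now could reach.

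**Conclusion.** The concern holds in two parts of unequal strength. The firm part is a contradiction over Grade 4 AST/ALT elevation at 160 mg: the 120 mg item in Section 7.4.6 disagrees with Table 7.4.6-1 and Section 8.1.4, and the exception lists for the 120 mg and 80 mg steps are inconsistent. The secondary part is a difference of default and condition between Sections 7.4.6 and 8.1.4 for other non-infection Grade 4 reactions at 160 mg or 120 mg, with precedence indicated but not stated.

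A reader might infer two stronger things that the documents do not support. One is that the sections flatly oppose each other on whether treatment may ever restart after a Grade 4 reaction; Section 8.1.4 itself provides for resumption. The other is that every Grade 4 regorafenib reaction is affected. Infection is exempt from both reduction items, hepatotoxicity at 120 mg is exempt, and failure at 80 mg raises no conflict.

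The number of participants affected is unknown. The 2.5-point step assumes the planned 40 participants, and the timing bound assumes exponential progression at the cited median. The point is worth correcting because it concerns a safety rule and the correction is cheap, not because it threatens the primary analysis.

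**What to change.** Reconcile the Section 7.4.6 lists, Table 7.4.6-1 and Section 8.1.4 so that each category of Grade 4 reaction has one instruction and the exception lists are consistent across the two dose steps. State how the permanent-stop heading of Section 8.1.4 relates to the resume clause beneath it. State which passage governs if they differ, and cross-reference Section 8.1.4 from Sections 7.4 and 7.4.6. Which instruction is clinically right is for the sponsor and its clinical advisers; no dose or rule is proposed here.

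The cost is a protocol clarification letter with no added procedures. For Cohort 5 Grade 4 reactions that have already occurred, the study report could list the action taken and the passage followed, so that the discontinuation summary can be interpreted.

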8.1.5 Treatment Beyond Progression

Participants in Cohorts 4 and 6 only, will be permitted to continue treatment beyond initial RECIST 1.1 defined progressive disease (PD), as assessed by the investigator, as long as the following criteria are considered:

- Investigator-assessed clinical benefit
- Tolerance of study drug
- Stable performance status
- Treatment beyond progression will not delay an imminent intervention to prevent serious complications of disease progression (eg, CNS metastases)
- Participant provides written informed consent prior to receiving additional treatment with the investigational study drug regimen. All other elements of the main consent including description of reasonably foreseeable risks or discomforts, or other alternative treatment options will still apply.
- Approval by Medical Monitor/designee.

Radiographic assessment/scan(s) should continue in accordance with the [Section 2](#) Schedule of Activities for the duration of the treatment beyond progression and should be submitted to the central imaging vendor.

If the investigator feels that the participant continues to achieve clinical benefit by continuing treatment, the participant should remain on the trial and continue to receive monitoring according to the Schedule of Activities, presented in [Section 2](#).

For the participants who continue study therapy beyond progression, further progression is defined as an additional 10% increase in tumor burden with a minimum 5 mm absolute increase from time of initial PD. This includes an increase in the sum of diameters of all target lesions and/ or the diameters of new measurable lesions compared to the time of initial PD. It is recommended that study treatment should be discontinued permanently upon documentation of further progression.

New lesions are considered measurable at the time of initial progression if the longest diameter is at least 10 mm (except for pathological lymph nodes which must have a short axis of at least 15 mm). Any new lesion considered non-measurable at the time of initial progression may become measurable and therefore included in the tumor burden if the longest diameter increases to at least 10 mm (except for pathological lymph nodes which must have a short axis of at least 15 mm). In situations where the relative increase in total tumor burden by 10% is solely due to inclusion of new lesions which become measurable, these new lesions must demonstrate an absolute increase of at least 5 mm.

8.1.6 Post Study Treatment Study Follow-up

Post study treatment follow-up is of critical importance and is essential to preserving participant safety and the integrity of the study. Participants who discontinue study treatment must continue to be followed until the LPLV on the study.

8.2 Discontinuation from the Study

Participants who request to discontinue study treatment will remain in the study and must continue to be followed for protocol specified follow-up procedures. The only exception to this is when a participant specifically withdraws consent for any further contact with him/her or persons previously authorized by participant to provide this information.

- Participants should notify the investigator of the decision to withdraw consent from future follow-up **in writing**, whenever possible.
- The withdrawal of consent should be explained in detail in the medical records by the investigator, as to whether the withdrawal is from further treatment with study treatment only or also from study procedures and/or post treatment study follow-up, and entered on the appropriate CRF page.
- In the event that vital status (whether the participant is alive or dead) is being measured, publicly available information should be used to determine vital status only as appropriately directed in accordance with local law.
- If the participant withdraws consent for disclosure of future information, the sponsor may retain and continue to use any data collected before such a withdrawal of consent.

8.3 Lost to Follow-Up

- All reasonable efforts must be made to locate participants to determine and report their ongoing status. This includes follow-up with persons authorized by the participant.
- Lost to follow-up is defined by the inability to reach the participant after a minimum of **three** documented phone calls, faxes, or emails as well as lack of response by participant to one registered mail letter. All attempts should be documented in the participant's medical records.
- If it is determined that the participant has died, the site will use permissible local methods to obtain date and cause of death.
- If investigator's use of third-party representative to assist in the follow-up portion of the study has been included in the participant's informed consent, then the investigator may use a Sponsor retained third-party representative to assist site staff with obtaining participant's contact information or other public vital status data necessary to complete the follow-up portion of the study.
- The site staff and representative will consult publicly available sources, such as public health registries and databases, in order to obtain updated contact information.
- If after all attempts, the participant remains lost to follow-up, then the last known alive date as determined by the investigator should be reported and documented in the participant's medical records.

